5.3. Application Modification

No modification of product application is permitted in this study.

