Image capture (VISIA) Post-Procedure, Post-Treatment ¹⁴				X				X
Subject Self-Assessment Post-Procedure, Post-Treatment ¹⁵			X	X	X	X	X	X
Subject Global Self-Assessment								X
Dermatologist Assessment Post-Procedure, Post-Treatment ¹⁵			X	X	X	X	X	X
Dermatologist Global Assessment of Tolerance								X
Supervised Test-Product Application ¹⁶				X	X	X	X	
Supervised Sunscreen Application ¹⁷				X	X	X	X	
Products and Test Diary Return								X
Discharge from Study								X

	Document Name	Post 207213721308F 20 Day Cream.doc		
	Type	Version	Document Identifier	Effective Date
	eldo controlled	0.0; CURRENT/Effective/Current	090032d580e2d8#6	07-Jun-2017 01:32:30
	Reason For Issue	Auto Issue		

1. For Visits 3-8, subjects will be instructed to cleanse their face at home using the cleanser provided and must not use any other product on their face, including the test product (Group I only) and sunscreen. Subjects will be instructed to bring the dispensed cleanser, sunscreen and test product (Group I only) with them to all visits. Subjects will be invited to the site in the morning (prior to 9 am) to avoid exposure to strong sunlight.
2. The Investigator or designee will review the diary to monitor and encourage compliance. Additional or missed product applications will be recorded as deviations. The Evaluator must be blind to diary review.
3. Exclusion Criteria 9 will not be included for this assessment. Exclusion criteria 9 is evaluated based on the results from the sensitivity test.
4. To include a review of the inclusion/exclusion criteria specified in Appendix 4. Subjects must be considered compliant with these inclusion/exclusion criteria in order to remain eligible for the study.
5. Peel regimen (70% Glycolic Acid facial peel solution, Bicarbonate Neutralizing Solution and Sunmax Sensitive SPF 50) to be applied to the volar forearm of each subject by a qualified dermatologist.
6. Assessments to be taken 45±15 minutes after completion of the study material sensitivity test.
7. Assessments to be taken 24±4 hours after completion of the study material sensitivity test.
8. Assessments to be taken 7 days after completion of the study material sensitivity test.
9. 70% Glycolic Acid facial peel to be administered by a qualified dermatologist who must be blind to randomization. The Glycolic Acid treatment and neutralizing solution will be sourced commercially by the study site.
10. Assessments to be taken 60±15 minutes after completion of the facial peel procedure.

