($p \leq 0.04$) from day 14 until the end of treatment, except at day 28 ($p \leq 0.07$). Evolutions of the functional symptoms (pain, itching, stinging and tightening) in the two groups were all statistically significantly improved compared to the post-procedure baseline ($p \leq 0.05$) after 3-4 weeks of treatment, although inter-group significance was only observed for mean itching (Day 28), stinging (Days 14 and 21) and tightening (Days 12 and 21). Investigator-assessed global efficacy and subject self-assessed global tolerance at the end of the study was statistically significantly in favour of the water group compared to placebo ($p \leq 0.05$). Three treatment-related local side-effects were reported during the study. One subject experienced an allergic contact dermatitis of undetermined origin and was withdrawn from the study at the 28-day visit. One subject presented peri-labial pustules and was withdrawn at Day 7. A third subject presented cleanser-imputed contact allergy at the end of study. No systemic adverse effects that were considered possible or probably related to test treatment were recorded for either group.

Narurkar (2010) conducted a 14-week open-label study to evaluate the efficacy and safety of a topical cosmetic skin care regimen for minimizing localized Adverse Events (AEs) during two 6-week procedure cycles with fractionated laser or intense pulsed light. The skin care regimen consisted of a 2-week pre-procedure phase, a 1-week post-procedure phase and a 3-week maintenance phase. Investigators and subjects rated the presence and severity of erythema, itching, stinging/burning, edema, pain, pruritus, swelling, crusts/erosions and photo-damage. Two days after each procedure, most assessments were near baseline values and at 4 weeks all investigator scores were comparable to baseline. Two weeks post-procedure, mean subject ratings for most endpoints were 'none' to 'mild'. Fourteen subjects reported a total of 16 AE's. Of these, 4 subjects (15%) reported AE's considered possibly related to the non-ablative cosmetic procedure or the test product regimen. These AE's included acne and facial rash and were mild in intensity. Two subjects withdrew from the study due to an AE. One subject had a severe rash was considered probably related to the study treatment and one subject developed shingles, which was considered unrelated to treatment.

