Schalka (2013) published the results of a clinical study which investigated the efficacy and safety of a novel cosmetic skin care product in subjects who underwent a 5% retinoic acid facial peel. This comparative, open-label clinical study randomized 52 subjects who were divided into two groups, with 26 subjects allocated to each group. One group was provided with a Sun Protection Factor (SPF) 30 cream (control) and the other group was provided with the test product and SPF 30 control. Regular clinical assessment and biophysical measurements were conducted for a

 GlaxoSmithKline	Document Name	090032d580e2d8a6 20 Day Cream.doc		
	Type	Version	Document Identifier	Effective Date
	eldo_controlled	0.0; Current Effective	090032d580e2d8a6	07-Jun-2017 01:32:30
	Reason For Issue	Auto Issue		

period of 1 week post-procedure. Fifty subjects completed the study, with one subject withdrawing for personal reasons and the other discontinued from the study due to the occurrence of mild contact dermatitis in the test product plus sunscreen group. Statistically significant ($p \leq 0.05$) cosmetic benefits were observed for clinically-assessed desquamation (Days 4 to 7) and instrumental Corneometer measurements (Days 2 to 4) for the treatment group over the control group. Crucially, the magnitude of cosmetic assessments between groups was numerically largest between days 2 and 4, presumably because the skin's natural repair processes were continually reducing the cutaneous damage for both groups, making it more difficult to measure a cosmetic benefit over time. Barrier function was observed to gradually worsen over the duration of the study, with weak indications of improvement between days 4 and 7. There was no statistically significant barrier function benefit between groups at any time point.

Based on this literature review, subject visits have been included at 24-72 hours post-procedure, where differences between control and test groups are expected to be largest. While it is expected the skin's barrier function will return to normal 24 to 48 hours following the procedure, the total duration of the test phase is 14 days to enable sufficient time to monitor desquamation and erythema compared to the post-procedure, pre-treatment baseline.

 GlaxoSmithKline	Document Name	GSK-207237-01-001F 20 Day Cream.doc		
	Type	Version	Document Identifier	Effective Date
	eldo_controlled	0.0: Current Effective/Current	090032d580e2d8a6	07-Jun-2017 01:32:30

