4.4. Withdrawal/ Stopping Criteria

A subject may withdraw from the study at any time at his/her own request, or may be withdrawn at any time at the discretion of the investigator for safety, behavioural or administrative reasons.

If the reason for removal of a subject from the study is an AE or an abnormal laboratory test result, the principal specific event or test will be recorded on the electronic Case Report Form (eCRF). If a subject is withdrawn from the study because of a product limiting AE, thorough efforts should be clearly made to document the outcome. Any AEs ongoing at the final visit will be followed up until resolved, the condition stabilizes, is otherwise explained, or the subject is lost to follow-up.

The following actions must be taken in relation to a subject who fails to attend the clinic for a required study visit:

- The site must attempt to contact the subject and re-schedule the missed visit as soon as possible.

 GlaxoSmithKline	Document Name	090032d580e2d8a6 20 Day Cream.doc		
	Type	Version	Document Identifier	Effective Date
	eldo_controlled	0.0; CURRENT Effective Date: CURRENT	090032d580e2d8a6	07-Jun-2017 01:32:30
	Reason For Issue	Auto Issue		

- The site must counsel the subject on the importance of maintaining the assigned visit schedule and ascertain whether or not the subject wishes to and/or should continue in the study.
- In cases where the subject is deemed ‘lost to follow up’, the investigator or designee must make every effort to regain contact with the subject (where possible, at least 2 telephone calls). The contact attempt should be documented in the subject’s record.
- Should the subject continue to be unreachable, only then will he/she be considered to have withdrawn from the study with a primary reason of “Lost to Follow-up”.

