6.8.14. Discharge from Study

Subjects will be evaluated to determine if they completed all study procedures or if they were discontinued from the study early. If the subject discontinued at any point during the study, the primary reason for withdrawal should be recorded on the Study Conclusion page of the eCRF by selecting one of the options below.

1. Subject did not meet study criteria
2. Adverse Event
3. Lost to Follow Up
4. Protocol Violation
5. Withdrawal of Consent
6. Other

 GlaxoSmithKline	Document Name	GSK2072107/01/001F 20 Day Cream.doc		
	Type	Version	Document Identifier	Effective Date
	eldo controlled	0.0: CURRENT/Effective/Current	090032d580e2d8a6	07-Jun-2017 01:32:30
	Reason For Issue	Auto Issue		

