9.2.6. Handling of Dropouts and Missing Data

Missing data will not be imputed. All data available for dropouts will be considered in analyses.

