Product Regimen was Well Tolerated	XX (XX%)	XX (XX%)
Product Regimen was Not Well Tolerated	XX (XX%)	XX (XX%)
95% Confidence Interval for Proportion Well Tolerated	(XX.X%, XX.X%)	(XX.X%, XX.X%)
Difference in Proportions Well Tolerated (95% Confidence Interval)		XX% (XX.X - XX.X)
Chi-Square P-Value		X.XXX

Percentages based on the total number of subjects per product group.

Program file name xxxxxxxxxxxxxxxxxxxxxx

Table 9.3.3.2.1
 Summary of Dermatologist Assessments - Total Score[®]- Changes from Baseline
 Safety Population

Safety Population (N=xx)

Timepoint		Physiogel Calming Relief	No Test Product
		SPF 20 Cream	
Pre-Procedure Assessment	N	XX	XX
	Missing	XX	XX
	Mean	X.XX	X.XX
	SD	X.XXX	X.XXX
	95%CI	X.XX, X.XX	X.XX, X.XX
Baseline*	N	XX	XX
	Missing	XX	XX
	Mean	X.XX	X.XX
	SD	X.XXX	X.XXX
	95%CI	X.XX, X.XX	X.XX, X.XX
180 Minutes Post-Procedure	N	XX	XX
	Missing	XX	XX
	Mean	X.XX	X.XX
	SD	X.XXX	X.XXX
	95%CI	X.XX, X.XX	X.XX, X.XX
Change from Baseline at 180 Minutes	N	XX	XX
	Missing	XX	XX
	Mean	X.XX	X.XX
	SD	X.XXX	X.XXX
	95%CI	X.XX, X.XX	X.XX, X.XX

	P-Value [‡]	X.XXX	X.XXX
Difference between Groups at	Difference	X.XX (X.XX, X.XX)	
180 Minutes	(95%CI)		
	P-Value [§]	X.XXX	
...		...	

[‡] Total score=sum of Erythema, Dryness, Desquamation/Peeling and Edema individual scores.

[‡] P-value from t-test or Wilcoxon signed rank test compared to zero.

[§] P-value from t-test or Wilcoxon rank sum test.

* Baseline score is assessed 60 minutes post-procedure and prior to any test product application.

Program file name xxxxxxxxxxxxxxxxxxxxxx

Programmers Note: Continue table for each timepoint. Same format for Tables 9.3.2.2.x, 9.3.3.2.x, 9.3.4 and 9.3.5 - Change the title, footnote and timepoints to match protocol.

7 Days

14 Days

Desquamation

Pre-procedure	X(xx%)	X(xx%)	X(xx%)	X(xx%)	X(xx%)	X	X(xx%)	X(xx%)	X(xx%)	X(xx%)	X(xx%)	X
Baseline* Score	X(xx%)	X(xx%)	X(xx%)	X(xx%)	X(xx%)	X	X(xx%)	X(xx%)	X(xx%)	X(xx%)	X(xx%)	X
180 Min	X(xx%)	X(xx%)	X(xx%)	X(xx%)	X(xx%)	X	X(xx%)	X(xx%)	X(xx%)	X(xx%)	X(xx%)	X
1 Day	X(xx%)	X(xx%)	X(xx%)	X(xx%)	X(xx%)	X	X(xx%)	X(xx%)	X(xx%)	X(xx%)	X(xx%)	X
2 Days	X(xx%)	X(xx%)	X(xx%)	X(xx%)	X(xx%)	X	X(xx%)	X(xx%)	X(xx%)	X(xx%)	X(xx%)	X
3 Days	X (xx%)	X (xx%)	X (xx%)	X(xx%)	X(xx%)	X	X (xx%)	X(xx%)	X(xx%)	X(xx%)	X(xx%)	X
7 Days	X (xx%)	X (xx%)	X (xx%)	X(xx%)	X(xx%)	X	X (xx%)	X(xx%)	X(xx%)	X(xx%)	X(xx%)	X
14 Days	X (xx%)	X (xx%)	X (xx%)	X(xx%)	X(xx%)	X	X (xx%)	X(xx%)	X(xx%)	X(xx%)	X(xx%)	X

Edema

Pre-procedure

Baseline* Score

180 Min

1 Day

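### A subject withdrawn for a skin reaction before Visit 8 falls under Missing, not Not Well Tolerated, in the primary tolerance table

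*Protocol*

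**What the plan says.** - **When the rating is made.** The protocol's Schedule of Events marks the "Dermatologist Global Assessment of Tolerance" at Visit 8 only, and SAP Appendix 1 does the same. No early-termination visit is scheduled.
- **What it measures.** Under protocol 6.8.12 and SAP 8.1, rating 1 covers clear, clinically relevant worsening of the expected effects of the peel, or any new and unexpected sign or symptom during product use.
- **What is asked for at withdrawal.** Protocol 4.4 begins "If a subject is withdrawn from the study because of a product limiting AE" and then requires efforts to document the outcome. Protocol 6.8.14 says "the primary reason for withdrawal should be recorded on the Study Conclusion page of the eCRF". Neither mentions the global rating.
- **Stopping the cream.** Protocol 5.3 reads "No modification of product application is permitted in this study".
- **Missing data.** Protocol 9.2.6 and SAP 5.4 say "Missing data will not be imputed".
- **The table.** SAP Table 9.3.1, on the Safety population, has separate rows for *Missing*, *Well Tolerated* and *Not Well Tolerated*. Its footnote is "Percentages based on the total number of subjects per product group". It also reports a confidence interval per group, a difference with its interval, and a chi-square p-value, without saying which subjects enter those.

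**The concern.** A skin reaction bad enough to end participation is the clearest sign of poor tolerance that this trial can produce, and rating 1 would be expected to apply to it. Yet the subject has left before the only visit at which the rating is made. The primary table can then show no intolerance at all while the intolerant subjects sit in the *Missing* row, next to subjects who moved away or withdrew consent. Protocol 5.3 contributes a little: nothing says that a reacting subject may stop the cream, stay in follow-up and be rated at Visit 8.

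At stake are the intolerance count of the primary endpoint and, depending on an unstated denominator, its confidence interval and the comparison between groups.

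**Working it through.** **The plan's own figure.** No sample size or power figure is given for the tolerance rating. The only one concerns the within-group TEWL change (SAP section 4: mean change 2.1, SD 4, n = 30, 80% power). A one-sample t-test reproduces it at 79.4%. It is not an input here.

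**Step 1: how often.** Protocol 3.4 describes three earlier studies with withdrawals for a reaction.

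- *Retinoic acid peel study, followed for 1 week.* One subject "discontinued from the study due to the occurrence of mild contact dermatitis in the test product plus sunscreen group". The arm had 26 subjects: 1/26 = 3.8%.
- *Laser study, followed for 84 days.* "One subject presented peri-labial pustules and was withdrawn at Day 7". A second subject left at the 28-day visit, which lies outside a 14-day test phase and is not counted: 1/74 = 1.4%. The two stated arms sum to 40 + 23 = 63, which would give 1/63 = 1.6%. The arm of the withdrawn subject is not given.
- *Open-label regimen study, 14 weeks.* One withdrawal for a severe rash. Four subjects are said to be 15%, so the total is about 4/0.15 = 27, and 1/27 = 3.7%. The timing is not given.

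With p from 1.4% (1/74) to 3.8% (1/26), the expected number is n × p and the chance of at least one is 1 − (1 − p)^n:

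| Test arm | Expected | Chance of at least one |
|---|---|---|
| 40 (80 randomised, assumed 1:1) | 0.5 to 1.5 | 42% to 79% |
| 30 (planned completers) | 0.4 to 1.2 | 34% to 69% |

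**Step 2: effect on the table.** Assume 40 per arm, k test-arm subjects withdrawn for a reaction and unrated, and everyone else rated well tolerated. Intervals are exact (Clopper-Pearson) and the chi-square is uncorrected.

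| | k = 2 | k = 4 |
|---|---|---|
| *Not Well Tolerated*, as planned | 0, with 2 *Missing* | 0, with 4 *Missing* |
| *Not Well Tolerated*, if rated 1 | 2/40 = 5.0% | 4/40 = 10.0% |
| *Well Tolerated*, all subjects | 38/40 = 95.0% (83.1 to 99.4) | 36/40 = 90.0% (76.3 to 97.2) |
| *Well Tolerated*, rated only | 38/38 = 100% (90.7 to 100) | 36/36 = 100% (90.3 to 100) |
| Against control 40/40, all subjects | p = 0.15 | p = 0.040 |
| Against control 40/40, rated only | no difference | no difference |

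For k = 4, chi-square = 80 × (36×0 − 4×40)² / (40 × 40 × 76 × 4) = 4.21, p = 0.040. Fisher's exact test gives 0.116, so the p-value depends on the test. The loss of the difference under the rated-only denominator does not.

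**Step 3: the success rule.** Protocol 9.2.3 needs more than 50% of the test product group, which is 21 of 40. The *Well Tolerated* count over all subjects is the same whether a withdrawal is *Missing* or *Not Well Tolerated*, so the rule is unaffected.

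**The case against.** The strongest reply is that no text forbids a rating at withdrawal. Protocol 6.8.12 speaks of rating each subject from all the data collected, 6.8.14 has early leavers evaluated at discharge, and 9.2.6 says that available dropout data will be used. This stands as far as it goes: a site could rate such a subject. But nothing asks it to, and a rule about using available data cannot supply a rating that was never made.

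It can also be said that the event is not hidden. That is correct. It appears as an adverse event discontinuation in Table 9.1, in the TEAE tables and in Listing 2.1, which flags withdrawal due to the event. The remaining fault is that the primary table needs cross-reading to be understood.

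Two stronger readings are tempting, and the documents do not support them.

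- *That the success proportion is inflated.* The rule refers to subjects in the test product group and the Table 9.3.1 footnote keeps missing subjects in the denominator. Only the interval and the chi-square have an unstated denominator.
- *That a subject who stops the cream but stays is lost as well.* Protocol 5.4 does not remove subjects for missed applications. She is rated at Visit 8 and counts in the primary Safety analysis. Non-compliance may exclude her from a per-protocol analysis, but that exclusion is a matter of blinded judgement. The 80% rule is worded differently in protocol 5.4 and 9.2.1. The analysis itself needs a difference of more than 10%, which is 5 of 40. At 3.8%, reaction stops alone reach that with probability 1.8%.

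**Conclusion.** The point holds as a gap in the primary tolerance table. Following the plan as written puts a subject withdrawn for a skin reaction before Day 22 under *Missing*, and the intolerance count is understated by the number of such subjects. The likely size is small: 0.5 to 1.5 in a test arm of 40. The trial's success conclusion does not change on the all-subjects denominator. The interval and the group comparison change only if they are computed on rated subjects, which the SAP leaves open.

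This rests on four assumptions: equal allocation of 80 subjects; precedent rates that carry over although procedure, product and duration differ; no rating made at withdrawal when none is requested; and a reaction that ends participation meeting rating 1, which remains the dermatologist's judgement. The example with 4 withdrawals lies above the expected number and serves to show the mechanism.

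**What to change.** 1. **Protocol 4.4, 6.8.12 and 6.8.14:** have the blinded dermatologist complete the global tolerance rating at early discharge, using the data collected to that point.
2. **SAP 8.1 and Table 9.3.1:** count a withdrawal for a local skin reaction with no rating as *Not Well Tolerated*, in both groups. State that the confidence intervals and the chi-square use all Safety subjects per group.
3. **Protocol 5.3:** allow a medically qualified investigator who does no blinded assessments to stop the cream for a skin reaction while the subject stays in follow-up. She then reaches Visit 8 and is rated in the usual way.

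Exempting such stops from per-protocol non-compliance for this rating is optional and minor.

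The cost is a few sentences in each document and one extra use of an existing form at discharge. The stop must be recorded where the blinded evaluator does not see it. A subject who leaves without a discharge assessment is classified by her withdrawal reason, which is cruder than a rating. With all Safety subjects in the denominator, subjects missing for unrelated reasons also count as not favourable in the interval and the test, as they already do in the table's percentages.

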5.4. Product Compliance

A daily diary will be used to monitor and promote compliance. Subjects will not be excluded due to missed applications, but will be reminded to use the products as per the instructions provided and to complete the diary card on a daily basis to encourage compliance. Missed or additional product applications will be recorded by the Investigator or designee as deviations. Subjects will be asked to bring their washout

 GlaxoSmithKline	Document Name	GSK267237/21308F 20 Day Cream.doc		
	Type	Version	Document Identifier	Effective Date
	eldo_controlled	0.0; Current Effective Date: 07-Jun-2017 01:32:30	090032d580e2d8a6	07-Jun-2017 01:32:30
	Reason For Issue	Auto Issue		

and test products to each site visit where it will be weighed to further confirm compliance with product usage.

To be considered compliant and part of the per-protocol (PP) population, a subject must have used the test product and/or sunscreen at least 80% of the instructed number of applications following completion of the facial peel procedure. **THE SUBJECT DIARY WILL BE USED AS THE PRIMARY DATA SOURCE WITH WHICH TO ASSESS SUBJECT COMPLIANCE.**

5.5. Precautions

No special precautions are required providing the study is carried out in accordance with this protocol.

5.6. Overdose

An overdose is a deliberate or inadvertent administration of a product at a dose higher than specified in the protocol.

Overdose is not likely to occur in this study. Limited quantities of the product will be supplied, and closely monitored by the site for each subject.

Overdose per se is not an AE. However, any clinical sequelae of an overdose should be reported as an AE (and serious adverse event (SAE), if appropriate). For reporting, follow the AE and SAE reporting instructions.

5.7. Rescue Therapy

No rescue therapy is required in this study.

5.8. Product Assignment

Subjects will be assigned to study product in accordance with the randomization schedule generated by the Biostatistics Department, GSKCH, prior to the start of the study, using validated internal software.

5.8.1 Randomization

A unique screening number will identify each subject screened for study participation. Screening numbers will be assigned in ascending numerical order as each subject signs their consent form. Subjects who meet all inclusion and exclusion criteria will be randomized according to the randomization schedule. Randomization numbers will be assigned in ascending numerical order as each subject is determined to be fully eligible.

 GlaxoSmithKline	Document Name	090032d580e2d8a6 20 Day Cream.doc		
	Type	Version	Document Identifier	Effective Date
	eldo_controlled	0.0; CURRENT Effective Date: CURRENT	090032d580e2d8a6	07-Jun-2017 01:32:30
	Reason For Issue	Auto Issue		

The investigator or designee will maintain a full record of study product accountability. A Product Dispensing Log must be kept current and will contain the following information:

1. The identification of the subject to whom the study product was dispensed.
2. The date(s) and quantity of the study product dispensed to the subject.
3. The date(s) and quantity of the study product returned by the subject (if applicable).

The inventory must be available for inspection by the study monitor during the study. At the end of the study, study product supplies will be verified by the monitor. Study product supplies will then be either collected by the study monitor or returned by the investigator or designee to the GSKCH Clinical Supplies Department or designated vendor.

